11.2 Administration of Test Preparations

Specific details of the IMP and NIMPs, and doses to be administered are provided in Section 5.2 and Section 8.1, respectively.

Part 1

On IMP dosing days (Day 1), subjects will be dosed in the morning and receive KD025 alone (Periods 1 and 4) or in combination with itraconazole (at the same time as IMP; Period 2), or rabeprazole (approximately 2 h prior to IMP; Period 3); a total of 240 mL water will be given immediately following oral administration. The exact time of dosing will be decided based on logistics and will be documented.

On NIMP dosing days, subjects will take treatments at approximately the same time each day with approximately 240 mL water. When NIMP is taken at home, subjects will record the time of administration in a diary card.

Subjects will receive a total of 4 single doses of KD025, each on a separate occasion and multiple doses of itraconazole, rabeprazole and rifampicin, on separate occasions, for 9, 4 and 9 consecutive days, respectively.

The minimum washout period between treatment periods may be changed, if data collected during the study support the change. However, the minimum washout period will not be reduced to less than 5 half-lives of the IMP.

Part 2

On Day 1, Period 1, subjects will be dosed in the morning and will receive KD025 alone with a total of 240 mL water given immediately following oral administration. A second dose of IMP will be administered approximately 12 h after morning dose.

On Day 1, Period 2, subjects will be dosed in the morning with the NIMP approximately 2 h prior to IMP administration. Approximately 240 mL of water will be given immediately following oral administration. A second dose of IMP will be administered approximately 12 h after morning IMP dose. When NIMP is taken at home, subjects will record the time of administration in a diary card.

All IMP doses in Part 2 will be given in the fed state, relative to dosing. See Section 11.1.1 for details.

The exact time of dosing will be decided based on logistics and will be documented.

Subjects will receive a single day BID (Q12h) dose of KD025 on 2 separate occasions, and single doses of omeprazole for 4 consecutive days.

The minimum washout period between treatment periods may be changed, if data collected during the study support the change. However, the minimum washout period will not be reduced to less than 5 half-lives of the IMP.

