KD025 was the main analyte detected in all clinical studies, with maximal plasma concentration (Cmax) ranging from ~100 ng/mL (20 mg once daily [QD] in SLx-2119-09-01) to ~5300 ng/mL (500 mg twice daily [BID] in KD025-102), and median time to maximal plasma concentration (Tmax) ranging from ~2 h to ~8 h. Cmax and the area under the concentration-time curve (AUC) appear to be slightly greater than dose responsive over the 20 to 500 mg QD, but less than dose linear for doses > 500 mg. The half-life typically ranged from 4 h to 8 h, with a few reports greater than 8 h.

Two metabolites, KD025m1 and KD025m2, rapidly appeared in plasma and were readily eliminated. A major metabolite, KD025m2, was detected at Cmax levels ~20% that of parent and AUC approximately 15% that of parent. A minor metabolite, KD025m1, was detected at Cmax levels <5% of parent and AUC ~2% parent. Accumulation of KD025m2 was reported after multiple doses. KD025m1 did not accumulate.

In both Study KD025-105 (a fed/fasted crossover study with KD025 capsules) and Study KD025-106 (a fed/fasted crossover study with KD025 tablets), a high-fat meal given 30 minutes prior to KD025 oral administration had a significant effect on the pharmacokinetics (PK) of KD025. Plasma systemic exposure (Cmax and AUCs) of KD025 was approximately 2- to 3-fold higher under the fed state compared with the fasted state, and the median Tmax value was delayed by 0.5 to 2 h with food.

6 Rationale

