6.2.2 Itraconazole

Itraconazole is recommended in the 2017 US Food and Drug Administration (FDA) Clinical Drug Interaction Studies guidance document as being a strong inhibitor of CYP3A4 [15]. From the literature, a dose of 200 mg QD for a duration of 4 days is commonly used to achieve clinically relevant inhibition of CYP3A4 [16][17][18]. Furthermore, a dose of 200 mg QD is the recommended clinical dosing regimen for itraconazole [19].

However, itraconazole has time dependent kinetics, thus after 15 days of multiple dosing at 100 mg and 200 mg QD or 200 mg BID, there is greater accumulation than would be predicted from the single dose kinetics, and the half-life is increased from around 15 to 25 h following single dosing, to around 35 to 40 h after multiple dosing [20]. Thus a dosing duration of 9 days was selected as a duration which would result in a clinically relevant inhibition of CYP3A4 with consideration given to the multiple dose kinetics of itraconazole.

Dosing of itraconazole in Period 2 will continue on Day 1 of dosing with KD025, and on Day 2, ie during the washout phase of KD025, in order to maintain CYP3A4 inhibition during the elimination phase of KD025.

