On the morning following admission for each period (Day 1), subjects will receive a single dose of IMP, either alone (Periods 1 and 4) or co-administered with NIMP (itraconazole in Period 2 [at the same time as IMP; fed state] and rabeprazole in Period 3 [2 h prior to IMP; fasted state]). In Period 2, a further dose of itraconazole will be administered on the day after IMP administration (Day 2). All subjects will remain on site until 48 h post-IMP dose for safety and PK assessments. There will be a minimum washout of 2, 8 and 4 days following completion of dosing in Periods 1, 2 and 3, respectively. A follow-up visit will take place 3 to 5 days post-final discharge.

The Part 1 study design is presented in Figure 1.

[figure not shown]

Figure 1 Part 1 Study Sequence

8.1.2 Study Plan Part 2

Part 2 is a single centre, non-randomised, 2-period sequential dose assessment in healthy male subjects. In each period, subjects will receive a single day of BID dosing with IMP (KD025 tablet) in the fed state. Additionally, in order to assess the effect of a modest increase in gastric pH on the exposure of KD025, subjects will also receive multiple QD doses of the NIMP omeprazole, a PPI, in Period 2:

Period	IMP/NIMP Dose
1	KD025 200 mg BID (Q12h) on a single day
2	omeprazole 20 mg QD for 3 days
	KD025 200 mg single day, BID (Q12h) + omeprazole 20 mg QD on 4th day

QD: once daily, BID: twice daily, Q12h: every 12 hours Details of the IMP and NIMPs are provided in Section 5.2

^a If the minimum washout period is extended, subjects will receive their first dose of itraconazole during a separate outpatient visit on Day -7 of Period 2

^b Subjects will take itraconazole (Period 2)/rifampicin (Period 4) in the clinic after admission

^c Subjects will take the evening dose of rabeprazole at home, prior to admission

It is planned to enrol 38 subjects to ensure there are 34 evaluable subjects, defined as those subjects who have sufficient PK data to assess the primary objective of Part 2 of the study.

All subjects will undergo preliminary screening procedures to determine their eligibility for the study at the screening visit (Day -28 to Day -2 of Period 1). For each period, subjects will be admitted to the clinic on the evening of the day prior to IMP administration (Day-1) for confirmation of eligibility and baseline procedures.

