11.1.2 Non-Investigational Medicinal Product Dosing

Part 1

Subjects will take itraconazole for 9 consecutive days; on Day 3 of Period 1 and from Day -6 to Day 2 of Period 2. All doses of itraconazole should be taken with approximately 240 mL water at approximately the same time each morning following breakfast; when co-administered with IMP on Day 1, a total of 240 mL water should be taken.

Subjects will take rabeprazole for 4 consecutive days; from Day -3 to Day 1 of Period 3. All doses of rabeprazole should be taken with approximately 240 mL water. On Days -3 to -1 (BID dosing days) subjects should take rabeprazole at approximately the same time each morning following breakfast, and following an evening meal. On Day 1, rabeprazole will be administered in the fasted state, approximately 2 h prior to IMP administration.

Subjects will take rifampicin for 9 consecutive days; from Day -9 to Day -1 of Period 4. All doses of rifampicin should be taken with approximately 240 mL water at approximately the same time each morning, prior to eating breakfast.

Part 2

Subjects will take omeprazole for 4 consecutive days; from Day -3 to Day 1 of Period 2. All doses of omeprazole should be taken with approximately 240 mL water. On Days -3 to -1 (Period 2 only) subjects should take omeprazole at approximately the same time each morning prior to eating breakfast. On Day 1, omeprazole will be administered in the fasted state, approximately 2 h prior to IMP administration. Decaffeinated fluids will not be allowed from 1 h prior until 1 h post-omeprazole administration (except on Day 1; see Section 11.1.1 Part 2 for details).

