On the morning following admission for each period (Day 1), subjects will receive a single dose of IMP, either alone (Periods 1 and 4) or co-administered with NIMP (itraconazole in Period 2 [at the same time as IMP; fed state] and rabeprazole in Period 3 [2 h prior to IMP; fasted state]). In Period 2, a further dose of itraconazole will be administered on the day after IMP administration (Day 2). All subjects will remain on site until 48 h post-IMP dose for safety and PK assessments. There will be a minimum washout of 2, 8 and 4 days following completion of dosing in Periods 1, 2 and 3, respectively. A follow-up visit will take place 3 to 5 days post-final discharge.

The minimum washout period between treatment periods may be changed, if data collected during the study support the change. However, the minimum washout period will not be reduced to less than 5 half-lives of the IMP.

The Part 1 study design is presented in Figure 1 below.

Figure 1 Part 1 Study Sequence

a If the minimum washout period is extended, subjects will receive their first dose of itraconazole during a separate outpatient visit on Day -7 of Period 2

b Subjects will take itraconazole (Period 2)/rifampicin (Period 4) in the clinic after admission

c Subjects will take the evening dose of rabeprazole at home, prior to admission

#### 5.1.2 Study Plan Part 2

Part 2 is a single centre, non-randomised, 2-period sequential dose assessment in healthy male subjects. In each period, subjects will receive a single day of BID dosing with IMP (KD025 tablet) in the fed state. Additionally, in order to assess the effect of a modest increase in gastric pH on the exposure of KD025, subjects will also receive multiple QD doses of the NIMP omeprazole, a PPI, in Period 2.

It is planned to enroll 38 subjects to ensure there are 34 evaluable subjects. A subject will be considered evaluable if they have sufficient data for evaluation of the primary objective of Part 2 of the study.

All subjects will undergo preliminary screening procedures to determine their eligibility for the study at the screening visit (Day -28 to Day -2 of Period 1). For each period, subjects will be admitted to the clinic on the evening of the day prior to IMP administration (Day -1) for confirmation of eligibility and baseline procedures.

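### In Part 1 the only numeric limit on shortening the washout is tied to the KD025 half-life and leaves out itraconazole, the longer-lived drug given before the rabeprazole period (minor)

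*Protocol*

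**What the plan says.** Protocol 8.1.1 fixes the Part 1 schedule: "There will be a minimum washout of 2, 8 and 4 days following completion of dosing in Periods 1, 2 and 3, respectively". Protocol 11.2 then adds a contingency: "The minimum washout period between treatment periods may be changed, if data collected during the study support the change". The next sentence limits it: "the minimum washout period will not be reduced to less than 5 half-lives of the IMP". SAP 5.1.1 repeats the limit: "However, the minimum washout period will not be reduced to less than 5 half-lives of the IMP". Neither document gives a limit based on the half-life of a co-administered drug. Protocol 11.2 uses the same text for Part 2, where only KD025 precedes the single washout.

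On KD025, Protocol 5.3.2 says: "The half-life typically ranged from 4 h to 8 h, with a few reports greater than 8 h". On itraconazole, Protocol 6.2.2 says: "the half-life is increased from around 15 to 25 h following single dosing, to around 35 to 40 h after multiple dosing". It ties the longer figure to 15 days of dosing. Protocol 11.1.2 sets the exposure that precedes the rabeprazole period: "Subjects will take itraconazole for 9 consecutive days; on Day 3 of Period 1 and from Day -6 to Day 2 of Period 2".

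Period 3 is compared with Period 1 in a fixed order, using a model with treatment and subject terms only (Protocol 15.4, SAP 9.2.4). The assays cover KD025 and its two metabolites (Protocol 13.1.1).

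**The concern.** In Part 1 the washout between Periods 2 and 3 has to clear a strong CYP3A4 inhibitor as well as KD025. A limit expressed in KD025 half-lives covers the shorter-lived of the two. If the washout were shortened to that limit, itraconazole would still be present when KD025 is given with rabeprazole.

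Protocol 6.1 describes CYP3A4 as predominant in KD025 metabolism. Residual inhibition would therefore be expected to raise KD025 exposure in Period 3 and understate the decrease caused by rabeprazole. Every subject follows the same order and there is no separate term for carry-over. The mock results table in SAP section 20 equates treatment with period. Any carry-over would be absorbed into the rabeprazole ratio, which is a Part 1 primary comparison.

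The requirement for supporting study data is a real condition, but it gives no direct check here, because itraconazole is not assayed.

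**Working it through.** **Inputs**
- KD025 half-life: 4 to 8 h (Protocol 5.3.2). The few longer reports would lengthen the limit.
- Itraconazole half-life: 35 to 40 h after multiple dosing, 15 to 25 h after a single dose (Protocol 6.2.2).
- Scheduled minimum washout after Period 2: 8 days = 192 h (Protocol 8.1.1).
- Rabeprazole lead-in, Day -3 to Day 1: 3 days = 72 h (Protocol 11.1.2).

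**Formula.** Assume first-order elimination: fraction remaining = 0.5^(t / half-life). This is an approximation, since Protocol 6.2.2 describes itraconazole kinetics as time dependent.

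**The scheduled 8 days.** The documents give no derivation, so there is no stated calculation to reproduce. As a consistency check, 5 × 35 = 175 h and 5 × 40 = 200 h, or 7.3 to 8.3 days. The 8-day minimum falls inside that range: 192/40 = 4.8 and 192/35 = 5.5 half-lives.

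**The limit.** 5 × 4 = 20 h and 5 × 8 = 40 h. In itraconazole half-lives this is 20/40 = 0.5 to 40/35 = 1.1.

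**How washout is counted.** Part 1 does not define the end point. In Period 1, KD025 is given on Day 1 and itraconazole starts on Day 3, with a 2-day minimum, which suggests counting to the first dose of the next co-administered drug. Protocol 8.1.2 says this outright for omeprazole in Part 2. On that assumption, KD025 in Period 3 follows the end of washout by about 72 h. The alternative, counting to the KD025 dose, is shown as well.

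**Itraconazole remaining at the Period 3 KD025 dose**

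| Washout | Counted to | Hours since last itraconazole dose | At 35 to 40 h | At 15 to 25 h |
|---|---|---|---|---|
| Scheduled 8 days | first rabeprazole dose | 192 + 72 = 264 | 0.5 to 1.0% | 0.1% or less |
| Scheduled 8 days | KD025 dose | 192 | 2.2 to 3.6% | 0.5% or less |
| At the limit | first rabeprazole dose | 20 + 72 = 92 to 40 + 72 = 112 | 10.9 to 20.3% | 0.6 to 7.8% |
| At the limit | KD025 dose | 20 to 40 | 45.3 to 70.7% | 15.7 to 57.4% |

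Examples for the third row: 0.5^(112/35) = 10.9%, 0.5^(92/40) = 20.3%, 0.5^(112/15) = 0.6%, 0.5^(92/25) = 7.8%.

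**From residual drug to bias.** The documents give no relation between itraconazole concentration and CYP3A4 inhibition, so these percentages cannot be turned into a bias in the ratio. Only its expected direction, upward, follows.

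**Could the conclusion change?** Protocol 6.1 reports a preliminary decrease of about 80% with rabeprazole in 21 subjects, a ratio near 0.20. Bringing the point estimate up to the lower acceptance limit would take a 0.70/0.20 = 3.5-fold increase, and the whole interval would have to move further still.

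**The case against.** The strongest reply is that nothing is wrong with the plan as scheduled. The 8-day minimum already matches about five itraconazole half-lives at the multiple-dose figure. The limit in Protocol 11.2 is a further restriction on top of a data-support condition, and does not itself permit a cut. The only washout change with operational provisions is an extension, and SAP 12.1 reports no change in study conduct. The 21 preliminary rabeprazole results show that some subjects had already passed this washout. All of this stands, and it makes the point minor.

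It is also fair that the 35 to 40 h figure follows 15 days of dosing and this study gives 9, so the residual may be lower. That is why the single-dose range is shown. Protocol 6.2.2 does, however, cite the multiple-dose kinetics in choosing nine days.

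A reader might infer that the passages flatly contradict each other. They do not: a scheduled minimum, a reported half-life and a looser outer limit can all hold at once. The weakness is a gap in what the limit covers. A reader might also infer that the washout could be cut to under 2 days at will. The data-support condition rules that out as a general statement. What remains is that the condition rests on data that do not include itraconazole.

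**Conclusion.** The point holds as a minor weakness in a contingency clause. The only numeric limit on shortening the Part 1 washout is 20 to 40 h on the protocol's KD025 figures, about 0.5 to 1.1 itraconazole half-lives at 35 to 40 h. Used to the full, it would leave about 11 to 20% of itraconazole at the Period 3 KD025 dose, or 0.6 to 8% at the single-dose half-life. This assumes first-order elimination and washout counted to the first rabeprazole dose. Counted to the KD025 dose, it would be 45 to 71% at 35 to 40 h.

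Two stronger conclusions are not supported. The scheduled design does not create material carry-over on these figures: 0.5 to 1.0% remains under the same counting, and nothing shows that the washout was shortened. Nor would carry-over be likely to reverse the rabeprazole finding. With a preliminary decrease of about 80%, it would distort the size of the estimate, by an amount that cannot be computed from the documents.

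**What to change.** Reconcile the Part 1 limit in Protocol 11.2 and SAP 5.1.1 with the itraconazole half-life in Protocol 6.2.2 and the 8-day minimum in Protocol 8.1.1, so that the limit on shortening also takes account of the drug co-administered in the preceding period. State in the same place which dose ends the washout in Part 1. The value is for the sponsor and investigator to set.

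The change is to wording in two documents. The planned schedule, sample size and analysis stay as they are. The cost is less freedom to shorten the washout, and the benefit is confined to any Part 1 subjects who have not yet reached Period 3.

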11.3 Dosing Compliance

During all clinical phases of the study, subjects will be observed by study staff to assure compliance to all study procedures, including dose administration.

Mouth and hand checks will be conducted after dosing to ensure the tablet/capsule has been swallowed.

When NIMP is taken at home, subjects will record the time of administration in a diary card.

The date and time that each subject is dosed will be recorded in the subject's source data. Any violation of compliance will require evaluation by the investigator and sponsor to determine if the subject can continue in the study.

11.4 Prior and Concomitant Medications

No medication will be permitted from 14 days before IMP administration until the follow-up visit except 4 g per day paracetamol and those deemed necessary by the investigator to treat AEs (see also Section 9.3). Any medications used will be recorded.

Emergency equipment and drugs will be available within the clinical unit as per current standard procedures. In the unlikely event that they are required, their use will be documented.

12 Assessment of Efficacy

Not applicable for this Phase I study.

13 Assessment of Pharmacokinetics and Pharmacodynamics

13.1 Assessment of Pharmacokinetics

13.1.1 Pharmacokinetic Blood Sampling

Venous blood samples will be withdrawn via an indwelling cannula or by venepuncture according to the time schedule presented in Appendix 2 and Appendix 3.

The acceptable deviations from the nominal post-dose blood sampling times are as follows:

- The pre-dose blood sample will be taken ≤1 h before dosing.
- 0 to 1 h post-dose samples will be taken within ± 2 min of the nominal post-dose sampling time
- >1 to 12 h post-dose samples will be taken within ± 10 min of the nominal post-dose sampling time
- >12 h post-dose samples will be taken within ± 30 min of the nominal post-dose sampling time

Samples will be collected into appropriate tubes as specified by the bioanalytical laboratory. Details of sample tubes and processing will be contained in the Clinical Sample Processing Manual.

Samples will be shipped to Covance Laboratories Ltd for the analysis of KD025 and metabolites KD025m1 and KD025m2.

13.2 Assessment of Pharmacodynamics

Not applicable for this Phase I study.

14 Assessment of Safety

14.1 Definition and Classification of Adverse Events

An AE is any untoward medical occurrence in a subject that occurs either before dosing (referred to as a pre-dose AE) or once a medicinal product has been administered, including occurrences which are not necessarily caused by or related to that product.

An adverse drug reaction is any AE where a causal relationship with the IMP is at least a reasonable possibility (possibly related or related).

Adverse events will be monitored from the time the subject signs the ICF until after the final follow-up call. The severity of AEs should be assessed as follows:

Mild An AE that is easily tolerated by the subject, causes minimal discomfort and does not interfere with everyday activities

Moderate An AE that is sufficiently discomforting to interfere with normal everyday activities; intervention may be needed

Severe An AE that prevents normal everyday activities; treatment or other intervention usually needed

14.2 Assessment of Causality

Every effort should be made by the investigator to try to explain each AE and assess its relationship, if any, to the IMP. The temporal relationship of the event to IMP administration should be considered in the causality assessment (ie if the event starts soon after IMP administration and resolves when the IMP is stopped).

Causality should be assessed using the following categories:

Unrelated: Clinical event with an incompatible time relationship to IMP

administration, and that could be explained by underlying disease or other drugs or chemicals or is incontrovertibly not

related to the IMP

Possibly related: Clinical event with a reasonable time relationship to IMP

administration, and that is unlikely to be attributed to concurrent

disease or other drugs or chemicals

Related: Clinical event with plausible time relationship to IMP

administration and that cannot be explained by concurrent

disease or other drugs or chemicals

The degree of certainty with which an AE is attributed to IMP administration (or alternative causes, eg natural history of the underlying disease, concomitant therapy, etc) will be determined by how well the experience can be understood in terms of one or more of the following:

- known pharmacology of the IMP
- reactions of a similar nature have been previously observed with the IMP or this class of drug
- the experience being related by time to IMP administration, terminating with IMP withdrawal or recurring on re-challenge
- alternative cause

